7.4 General Biostatistical Approaches

For the pregnancy tests based on hCG and hCG+ β levels, ROC analyses will be performed. The predicted results of the test (positive or negative, i.e. pregnant or not pregnant) will be compared to the actual presence/absence of pregnancy as observed (e.g. clinical pregnancy on day 21* (+4/-3) or ongoing pregnancy on day 65 (+7)). There are the following possibilities for the test results and observed results:

		Observed	
		Positive	Negative
Test	Positive	True positive (TP)	False positive (FP)
	Negative	False negative (FN)	True negative (TN)

For the test concerned, the rate of true positives and true negatives can be regarded in two different ways: in relation to the observed positives and negatives and in relation to the predicted positives and negatives.

Based on the observed positives and negatives, the rate of true positives is called the **sensitivity** and the rate of true negatives is called **specificity**, i.e.:

$$\text{Sensitivity} = \text{TP} / (\text{TP} + \text{FN})$$

$$\text{Specificity} = \text{TN} / (\text{TN} + \text{FP})$$

Based on the predicted positives and negatives, the rate of true positives is called the **positive predictive value (PPV)**, and the rate of true negatives is called the **negative predictive value (NPV)**, i.e.:

$$\text{PPV} = \text{TP} / (\text{TP} + \text{FP})$$

$$\text{NPV} = \text{TN} / (\text{FN} + \text{TN})$$

Sensitivity, specificity, positive and negative predictive values are all dependent on the definition of the test concerned. Receiver operating characteristics (ROC) curves are used to visualize sensitivity and specificity for various thresholds for the pertinent test: Sensitivity is plotted against 1-specificity and thus displays the test's characteristics for various cut-offs. Tests can be compared by looking at summary measures for the ROC curves, e.g. the area under the curve (AUC). Since high sensitivity and specificity are wanted in a test, a bigger area under the curve is desirable.

To define a test for practical use, a threshold has to be chosen, i.e. a cut-off that defines that values below are considered as negative test results and values above as positive test results. A threshold should be chosen as a point that optimizes the combination of sensitivity and specificity which can be done via the ROC curve by choosing the point with the least distance to the upper left corner which stands for specificity = 100% and sensitivity = 100%.

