7.5 Descriptive Statistics

Continuous variables will be summarized by descriptive statistics (mean, standard deviation, median, Q1, Q3, minimum, maximum, number of available data); categorical variables will be summarized by absolute and relative frequencies and number of available data. The relative frequencies will be based on the number of available data if not mentioned otherwise.

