7.6 Analysis by Study Objectives

7.6.1 Primary study Objective

The primary study objective is to determine, based on the AUCs of the ROC curves, whether serum hyperglycosylated human chorionic gonadotropin (hhCG) measured on day 4 (+1) after embryo transfer (ET) is superior to hCG+ β measured on day 4* (+1) in predicting clinical pregnancy on day 21* (+4/-3) (=6 weeks after last menstruation, detection of embryo sac by US).

The empirical AUCs, pertinent standard errors and 95% confidence intervals will be estimated for both the hhCG test and the hCG+ β test. Furthermore, the empirical AUCs of the two tests will be compared using a logistic regression model and the difference in AUCs will be estimated including 95% confidence intervals and chi-square test for the contrast. hhCG measured on day 4 (+1) after ET is considered superior to hCG+ β if the null hypothesis

$$H_0: \text{AUC (hhCG)} \leq \text{AUC (hCG+}\beta\text{)}$$

can be rejected at an one-sided significance level of 0.025.

The empirical ROC curves will be plotted to provide a visualization that supports the comparisons.

*Counted from ET (=Day 0).

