7.6.2 Secondary Study Objectives

In addition to the comparison of the AUCs under the ROC curves for day 4*, the same analyses will be performed for the hhCG and hCG + β tests at days 7 and 11 with respect to predicting clinical pregnancy on day 21*; at days 4, 7 and 11 with respect to predicting pregnancy on day 65; at days 4 and 7 with respect to predicting pregnancy on day 11. The same methods as for the analysis of the primary objective will be applied here.

For the comparisons of sensitivity and specificity and the positive and negative predictive values at various time points with respect to pregnancy at various later time points, the following approach will be used:

Optimal thresholds for the two tests and the various time points will be identified from the pertinent ROC curves for the time point (day 4, 7 or 11) and endpoint (pregnancy at day 65,

21 or 11) considered. The optimal threshold for the time point and test at hand will be found using Youden's index (sensitivity + specificity -1), choosing the point for which the index is maximal.

The thresholds and the corresponding sensitivities and specificities will be summarized for each time point, pregnancy endpoint and test. Pertinent positive and negative predictive values will be shown for the same thresholds for the various time points.

The course of hhCG and hCG + β over time will be summarized by descriptive summary statistics (mean, standard error of the mean, median, Q1, Q3, minimum and maximum) for the disjoint pregnancy outcome categories as defined in 5.1. If there are sufficiently many multiple pregnancies, the same analysis will be performed for the categories of multiple and single pregnancies (irrespective of pregnancy outcome).

Incidents and indirect harms will be summarized by absolute and relative frequencies.

*All days mentioned in this section are counted from ET (=Day 0).

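### Section 7.6.2 reports sensitivity, specificity, PPV and NPV in the same patients whose data chose the Youden cut-off, and plans neither an optimism correction nor confidence intervals for them

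*Combined protocol and SAP*

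**What the plan says.** Secondary objectives 4 and 5 in the synopsis are to compare sensitivity, specificity, PPV and NPV of hhCG and hCG+β and to identify cut-off values. Section 7.6.2 carries this out in three steps:

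- The cut-off for each test, day and endpoint comes from the corresponding ROC curve of this study, by Youden's index: "sensitivity + specificity -1), choosing the point for which the index is maximal".
- Two of the four measures are then tabulated in those same patients: "The thresholds and the corresponding sensitivities and specificities will be summarized for each time point, pregnancy endpoint and test".
- The other two are read off at the cut-offs already chosen: "Pertinent positive and negative predictive values will be shown for the same thresholds for the various time points".

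Confidence intervals appear elsewhere, for a different quantity. Section 7.6.1 states: "The empirical AUCs, pertinent standard errors and 95% confidence intervals will be estimated for both the hhCG test", with the same for hCG+β, and it adds an interval for the AUC difference. Section 7.6.2 extends this to the secondary AUCs ("The same methods as for the analysis of the primary objective will be applied here"). That sentence closes the AUC paragraph, and the four cut-off measures then get their own procedure, which names no interval. For other data, section 7.5 says only that "categorical variables will be summarized by absolute and relative frequencies and number of available data".

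No split sample, cross-validation, bootstrap, external cohort or pre-set cut-off is mentioned. Section 7.3 refers to a Statistical Analysis Plan, but only for further subgroups.

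**The concern.** The Youden cut-off is the point on the observed curve where sensitivity plus specificity happens to be largest. Part of that maximum is chance. Measured again in the same patients, accuracy at that point is too high on average, and the cut-off would do less well in new patients.

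The days and endpoints listed in section 7.6.2 give 3 days x 2 endpoints + 2 days x 1 endpoint = 8 combinations. For two tests that is 16 searched cut-offs, and with four measures each, 64 accuracy figures. Followed exactly, the plan reports all 64 with no correction and no stated uncertainty. Yet sensitivity, specificity and predictive values at a named cut-off are what a clinical reader is most likely to take away. Sections 1.2.2 and 2.1.2 call the study a proof of concept, but no sentence says that the cut-offs themselves are exploratory or need validation.

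**Working it through.** **Inputs.** Section 7.1 gives AUC 0.67 (hCG+β) and 0.79 (hhCG), 61 pregnant and 75 not pregnant, correlation 0.6, the binormal model and one-sided alpha 0.025. The SD ratio (pregnant to non-pregnant) is not given and is assumed to be 1 to 2.

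**The plan's own figure.** Section 7.1 states no accuracy at a cut-off, so its power figure serves only to check the inputs. The Hanley-McNeil variance is V(A) = [A(1-A) + 60(A/(2-A) - A²) + 74(2A²/(1+A) - A²)] / (61 x 75).

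- V(0.67) = 10.077/4575 = 0.002203, and V(0.79) = 7.312/4575 = 0.001598.
- A correlation of 0.6 between the markers implies about 0.57 between the AUCs.
- Null SD of the difference = √(2 x 0.002203 x 0.43) = 0.0435. Alternative SD = √(0.002203 + 0.001598 - 2 x 0.57 x √(0.002203 x 0.001598)) = 0.0408.
- Power = Φ((0.12 - 1.96 x 0.0435)/0.0408) = Φ(0.85) = 0.80, against 0.8022 stated. Other variance conventions give 0.83 to 0.86.

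**Best attainable index (equal SDs).** The separation of the means is d = √2 Φ⁻¹(AUC), and the largest true Youden index is 2Φ(d/2) - 1. For AUC 0.67 this is 2 x 0.622 - 1 = 0.244. For AUC 0.79 it is 2 x 0.716 - 1 = 0.431.

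**Optimism.** In each of 10,000 simulated trials (equal SDs, 61/75) the cut-off maximised the Youden index. Apparent values in those patients were compared with true values at the same cut-off. Averages:

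| | AUC 0.67: reported / true | AUC 0.79: reported / true |
|---|---|---|
| Sensitivity | 0.659 / 0.608 | 0.747 / 0.704 |
| Specificity | 0.652 / 0.619 | 0.738 / 0.711 |
| PPV | 0.622 / 0.576 | 0.709 / 0.674 |
| NPV | 0.714 / 0.670 | 0.789 / 0.754 |
| Youden index | 0.312 / 0.227 | 0.485 / 0.415 |

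The reported index even exceeds the best attainable one (0.312 against 0.244; 0.485 against 0.431). With SD ratios of 1 to 2, separate runs of 8,000 trials per setting gave an overstatement of 0.062-0.083 (AUC 0.67) and 0.056-0.070 (AUC 0.79). The reported index exceeded the true one in 80-89% of trials.

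**Other settings (assumed, because the documents give no figures).** With 41 to 82 positives of 136, to represent the day-11 and day-65 endpoints, the overstatement is 0.06-0.09 in the index and 2-6 points per measure. With higher AUCs, as may hold on days 7 and 11, it is 0.05-0.06 at AUC 0.87 and 0.04-0.05 at 0.95.

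**Against sampling error.** The exact (Clopper-Pearson) 95% interval for 44/61 = 0.72 is 0.59 to 0.83, half-width (0.829 - 0.592)/2 = 11.8 points. For 54/75 = 0.72 it is 0.60 to 0.82, half-width (0.818 - 0.604)/2 = 10.7 points. The largest bias in the table is 5.1 points (sensitivity, AUC 0.67), and 5.1/11.8 = 0.43.

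**Contrast between tests.** From the table, the reported difference in index is 0.485 - 0.312 = 0.173 and the true difference is 0.415 - 0.227 = 0.188, a bias of -0.015. Paired simulation with correlation 0.6 and SD ratios 1 to 2 gave -0.004 to -0.013. Both run slightly against hhCG.

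**Remedies checked (61/75).**

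- A bootstrap that repeats the search removed 68-76% of the index optimism.
- Repeated 10-fold cross-validation came within 0.01 of the true index (for example 0.226 against 0.227, and 0.422 against 0.417). This was checked for the mean index only.
- Plain exact intervals covered true sensitivity or specificity in 91-96% of trials. Most misses were on the optimistic side: the true value lay below the lower limit in 4-8%, not 2.5%. Lowering the limits by the estimated optimism raised coverage to 94-97%.
- For PPV and NPV, plain exact intervals already covered 97% or more.
- Unshifted percentile bootstrap intervals for the index covered only 61-76%.

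**The case against.** The strongest reply is that little depends on these figures. They are secondary and only summarised, in a study that calls itself a proof of concept. hhCG results stay unknown until study end, so no cut-off is applied to a patient. The bias is small beside sampling error. All of this stands. It limits the weight of the point, but it does not supply the missing intervals or label the cut-offs.

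A second reply is that the choice of correction is partly taste, and that shifted exact limits rest on simulation without ties or values at an assay limit. This also stands in part: plain exact limits are adequate for PPV and NPV, and the shift is only a refinement for sensitivity and specificity. Intervals might also be specified in a separate analysis plan, so the claim is confined to the supplied text.

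Three stronger readings are tempting, and the documents do not support them:

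- *The primary result is compromised.* The primary test in section 7.6.1 compares AUCs and uses no cut-off.
- *The cut-offs are meant for clinical use.* Section 7.4 does say "To define a test for practical use, a threshold has to be chosen", but this is general explanation of ROC methods, not a stated use of this study's cut-offs.
- *Sections 7.4 and 7.6.2 prescribe conflicting cut-off rules.* Section 7.4 describes a choice "which can be done via the ROC curve by choosing the point with the least distance to the upper left corner". That wording is permissive, and section 7.6.2 fixes the Youden rule, so there is no contradiction.

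**Conclusion.** The point holds for the secondary objectives that identify cut-offs and compare accuracy at them. Followed exactly, section 7.6.2 yields accuracy figures that are too high on average and carry no interval. At the planned 61/75 split and the day-4 AUCs, the overstatement is about 0.06 to 0.08 in the Youden index and 2 to 5 points per measure. This rests on the binormal model and the assumed SD ratio of 1 to 2. The size for the other days and endpoints depends on AUCs and counts that the documents do not give.

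A reader might infer that the search flatters hhCG. It does not: optimism is slightly larger for the weaker test, so the contrast moves by at most about 0.015 in the index, against hhCG. The change is worth making because it is cheap, not because any stated conclusion of the study is at risk.

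**What to change.** Add to section 7.6.2:

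1. Beside the apparent values, report optimism-corrected sensitivity, specificity, PPV and NPV from a bootstrap or repeated cross-validation that repeats the Youden search in every resample or training set.
2. Give exact binomial 95% confidence intervals for all four measures, with a note that for sensitivity and specificity they do not fully reflect the choice of cut-off. Lowering those limits by the estimated optimism is an optional refinement and is not needed for PPV and NPV. Do not use unshifted percentile bootstrap limits.
3. State that the cut-offs are exploratory and need validation in independent patients.

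The cost is a few sentences and a short resampling program, with no added patients, visits or assays. The corrected accuracy will look about 2 to 5 points less favourable per measure.

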PRIMARY PURPOSE	Utility of the hhCG assay (Quest Diagnostics), early after In Vitro Fertilization and fresh or frozen Embryo Transfer (IVF-ET), as aid in the prediction of ongoing pregnancy
STUDY OBJECTIVES	
Primary objective:
 
To determine, based on the AUCs of the ROC curves, whether serum hyperglycosylated human chorionic gonadotropin (hhCG) measured on day 4 (+1) after ET* is superior to hCG+β measured on day 4 (+1) in predicting clinical pregnancy on day 21 (+4/-3) (=6 weeks after last menstruation, with detection of embryo sac by US).
 
*ET= Embryo Transfer; all days mentioned in the following are counted from ET (=Day 0).

	
Secondary objectives*:
 
 1. To determine, based on the AUC of the ROC curves, whether hhCG measured on day 7 (+1) and day 11 (+2) is superior to hCG+β measured on the same days in predicting clinical pregnancy on day 21 (+4/-3) 2. To determine, based on the AUC of the ROC curve, whether hhCG measured on day 4 (+1), day 7 (+1) and day 11 (+2) is superior to hCG+β measured on the same days in predicting ongoing pregnancy on day 65 (+7) . 3. To determine, based on the AUC of the ROC curve, whether hhCG measured on day 4 (+1) and day 7 (+1) is superior to hCG+β measured on the same days in predicting pregnancy on day 11 (+2) defined by serum hCG+β. 4. To compare the sensitivity and specificity and the positive and negative predictive value of hhCG with hCG+β measured on days 4 (+1), 7 (+1) and 11 (+2) for clinical pregnancy on day 21 (+4/-3) and ongoing pregnancy on day 65 (+7) and to identify cut-off values. 5. To compare the sensitivity and specificity and the positive and negative predictive value of hhCG with hCG+β measured on days 4 (+1) and 7 (+1) for pregnancy on day 11 (+2) defined by serum hCG+β and to identify cut-off values. 6. To determine, based on the AUCs of the ROC curves, whether changes in hhCG on day 7 (+1) vs. day 4 (+1) and day 11 (+2) vs. day 7 (+1) are superior to corresponding

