STUDY POPULATION & TOTAL NUMBER OF PATIENTS	
A sample size of n= 136 patients eligible for the per-protocol analysis has been calculated of whom n=61 are expected to present with clinical pregnancy on day 21* (+4/-3). Based on an assumed rate of 10% patients enrolled but ineligible for the per-protocol analysis, n=152 patients are planned to be included in the study.
 
*Counted from ET (=Day 0).

NO. OF SITES	Monocentric study
SCHEDULE OF ASSESSMENTS	See Schedule of Assessments below
SAFETY	
As the only impact on patient safety by the study is from taking two additional blood samples, a general AE collection and assessment will not be carried out. Any AEs occurring in temporal relationship to drawing the two blood samples in addition to the study site's clinical routine will be documented observing the rights of patients' compensation for damage through participation in the study and the requirements of the insurance policy taken out. Incidents in connection with the diagnostic test will be documented following EU and local regulations and guidelines. Indirect harms to the patients are not possible to occur as the test result will only be known after individual study end. Hence, any incorrect results of the test can have no consequence for the further course of the patient during the study.

COMPLIANCE STATEMENT	
The study will be conducted in compliance with the Guidelines for Good Pharmacoepidemiology Practices (GPP) and applicable regulatory requirements.

Schedule of Assessments

	Screening	Visit 1	Visit 2	Visit 3	Visit 4	Visit 5	Visit 6
Days from ET ¹		Day 4 (+1)	Day 7 (+1)	Day 11 (+2)	Day 21 (+4/-3)	Day 28 (+4/-3)	Day 65 (+7)
Patient information	●						
Informed consent ²	●						
Demogr. data, Med. hist. ³	●						
Body weight and height	●						
Concomitant diseases	●	●	●	●	●	●	
Concomitant medication	●	●	●	●	●	●	
Incl. / excl. criteria	●						
Number of embryos transferred	●						
Serum estradiol, progesterone		●	●	●			
(Serum) hhCG, hCG+β ⁴		●	●	●			
Ultrasound ⁵					●	●	
Pregnancy category							●
Incidents and indirect harms							●
Final documentation ⁶							●

1 Embryo Transfer = day 0

2 Leaving the patient ample time for consideration after patient information has taken place

3 Including previous pregnancies and complications/outcomes

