7 SAMPLE SIZE AND STATISTICAL ANALYSIS

7.1 Sample Size Calculation

The two tests hhCG and hCG+ β will be compared using receiver operating characteristics (ROC) curves by analyzing the area under the curve (AUC). Based on the data by Chuan S et al. [16], an AUC of 0.67 is assumed for the hCG+ β test and an AUC of 0.79 for the hhCG test. Under the assumption that 45% of all patients with IVF will present with clinical pregnancy on day 21* (+4/-3), 136 patients are necessary to achieve 80% power for a one-sided z-test with significance level alpha = 2.5%.

Power	N+ *	N- **	AUC1	AUC2	Correlation
0.8022	61	75	0.6700	0.7900	0.6

* Pregnancies

** No Pregnancies

The results are for tests with continuous values and are based on the methodology of Hanley and McNeil (1983). The calculations are further based on the binormal model and the assumption of a correlation of 0.6 between the two tests for both the positive and negative groups (N+ and N-). Allowing for 10% of patients being non-evaluable, 152 patients are planned to be enrolled.

*Counted from ET (=Day 0).

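### Secondary objectives 4 and 5 promise a comparison of sensitivity and specificity, but 7.6.2 only lists each test at its own data-chosen Youden cut-off, so either measure taken singly is often in the wrong order

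*Combined protocol and SAP*

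**What the plan says.** The synopsis words secondary objectives 4 and 5 as comparisons: "To compare the sensitivity and specificity and the positive and negative predictive value of hhCG with hCG+β". Objective 4 takes days 4, 7 and 11 against clinical pregnancy (day 21) and ongoing pregnancy (day 65). Objective 5 takes days 4 and 7 against pregnancy on day 11. Both also ask for cut-off values to be identified.

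Section 7.6.2 presents its approach as serving these comparisons. It has two steps:

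- For each test, time point and endpoint, the threshold is the one that maximises Youden's index on that test's own ROC curve.
- The results are then tabulated: "The thresholds and the corresponding sensitivities and specificities will be summarized for each time point, pregnancy endpoint and test". For the predictive values: "Pertinent positive and negative predictive values will be shown for the same thresholds for the various time points".

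No difference between the tests, interval, paired analysis or common operating point is mentioned. The estimated difference with 95% confidence interval and chi-square contrast in 7.6.1 is for AUCs. The sentence in 7.6.2 that carries the primary methods over to secondary objectives closes the AUC paragraph, before the approach for sensitivity and specificity begins.

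Two further facts matter. Section 7.4 gives a different cut-off rule, the point nearest the upper left corner of the ROC plot. And objectives 8 and 9, which ask for the same comparison of changes between days, have no threshold method in 7.6.2, which sets thresholds only for the day 4, 7 and 11 values.

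**The concern.** Sensitivity and specificity trade off along a ROC curve. If each test is placed at its own optimum, a higher sensitivity for one may reflect only a lower specificity, and the reverse. With about 61 pregnancies and 75 non-pregnancies the empirical Youden point also moves a good deal by chance. A reader who takes the table as the promised comparison, and looks at sensitivity or specificity alone, can easily read the wrong order, with no interval to show how uncertain the gap is. Both tests are measured in the same women, so a paired estimate is available and goes unused.

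At stake is the answer to objectives 4 and 5. A trial that meets its primary AUC objective could also publish a table in which hhCG appears less sensitive, or less specific, than hCG+β.

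**Working it through.** **Inputs (section 7.1 and synopsis).** "an AUC of 0.67 is assumed for the hCG+ β test and an AUC of 0.79 for the hhCG test"; correlation 0.6 between the tests in both groups; 45% pregnant, so 136 × 0.45 = 61.2, giving 61 positive and 136 − 61 = 75 negative; one-sided alpha 0.025; stated power 0.8022. *Assumption:* equal variances in the two groups. The protocol says only that the model is binormal.

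**Step 1. Reproduce the stated power.** Hanley–McNeil variance, with Q₁ = A/(2−A) and Q₂ = 2A²/(1+A):

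Var(A) = [A(1−A) + (61−1)(Q₁−A²) + (75−1)(Q₂−A²)] / (61 × 75)

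- A = 0.67: Q₁ = 0.5038, Q₂ = 0.5376, Var = 0.002203, SE = 0.0469
- A = 0.79: Q₁ = 0.6529, Q₂ = 0.6973, Var = 0.001598, SE = 0.0400

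A score correlation of 0.6 corresponds to a correlation of about 0.57 between the AUC estimates.

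- Null variance (both AUCs 0.67): 2 × 0.002203 × (1 − 0.57) = 0.001894, root 0.0435
- Alternative variance: 0.002203 + 0.001598 − 2 × 0.57 × 0.0469 × 0.0400 = 0.001662, root 0.0408
- z = (0.12 − 1.96 × 0.0435)/0.0408 = 0.851, so power = 0.803

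This agrees with 0.8022. Other variance choices give somewhat different power (for example 0.82 to 0.87), but the planning values are understood.

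**Step 2. True values at the operating points.** With equal variances the group separation is d = √2 · Φ⁻¹(AUC). The true Youden point lies midway, where sensitivity = specificity = Φ(d/2). At 80% specificity, sensitivity = Φ(d − 0.842).

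| | hCG+β | hhCG |
|---|---|---|
| AUC | 0.67 | 0.79 |
| d | 0.622 | 1.140 |
| Sensitivity = specificity at true Youden point | 0.622 | 0.716 |
| Sensitivity at 80% specificity | 0.413 | 0.617 |

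So hhCG is truly better on both measures, by 9 points each at the Youden points, and by 20 points of sensitivity at a common 80% specificity.

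**Step 3. Simulate the 7.6.2 procedure.** 20,000 trials of paired binormal scores, 61 and 75 women, with the empirical Youden cut-off chosen separately for each test. How often hhCG comes out lower:

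| Measure | Share of trials |
|---|---|
| Sensitivity | 29% |
| Specificity | 29% |
| At least one of the two | 58% (57% in smaller separate runs) |
| Both | 0.05% |
| Youden index | 0.9% |
| AUC | 0.1% |
| PPV / NPV | 13% / 14% |

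The SD of sensitivity at the Youden point is 0.14 for hCG+β and 0.10 for hhCG. The central 95% range of the observed sensitivity difference is −25 to +41 points. Among trials in which the AUC test is significant for hhCG, 55% still show it lower on at least one of the two measures.

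**Step 4. Sensitivity to assumptions** (sensitivity/specificity reversed):

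- Correlation 0.3: 30%/30%. Correlation 0.8: 27%/27%.
- AUC 0.67 vs 0.87, the pair that section 1.2.1 reports for the earlier retrospective study: 16%/16%.
- AUC 0.79 vs 0.85: 32%/33%.
- Pregnant-group SD 1.5 or 2 times the other: at least one lower in 57% and 52%, shifted towards specificity, where the true gap may be smaller.
- Upper-left-corner rule of 7.4: 14%/14%, at least one 27%.

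**Step 5. Do the remedies work?** Comparing sensitivity at a common specificity gives the wrong sign in under 2% of trials at 80%, about 3% at 90%, and about 5% to 6% at 95%. A McNemar test at the two separate Youden cut-offs is nominally significant for the worse test in 10% of trials for sensitivity and 12% for specificity.

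**The case against.** The strongest defence is that nobody is asked to rank the tests from this table. Section 7.6.2 applies the AUC contrast, with interval and test, to the same days and endpoints as objectives 4 and 5. Those objectives say compare, where others ask about superiority, and they also ask for cut-off values. Each test would need its own threshold in use, as 7.4 recognises, so showing each at its own optimum is a legitimate description. The study is a proof of concept and these analyses are secondary.

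Most of this stands, and it limits the point. A reader might infer that the method often ranks the better test as worse. The calculations do not support that: both measures reverse together in about 0.05% of trials and the Youden index in under 1%. A loss on one measure is almost always offset by a gain on the other, and the listed pair shows it. A reader might also infer that the missing paired test is the root of the problem. It is not: separately optimised cut-offs are the cause, and a paired test at those cut-offs can favour the worse test. Finally, one might suppose that objectives 8 and 9 are covered by the Youden listing. Section 7.6.2 sets no thresholds for changes, which is a separate gap.

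What the defence does not answer is that 7.6.2 offers this listing as the method of comparison and gives no difference or uncertainty for any of the four measures.

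**Conclusion.** The point holds for objectives 4 and 5. The plan promises a comparison of sensitivity, specificity, PPV and NPV and delivers a side-by-side listing at separately chosen, data-driven cut-offs. At the planning values, sensitivity and specificity are each in the wrong order in about 29% of trials under the Youden rule and about 14% under the rule in 7.4; at least one is wrong in about 57% and 27% respectively.

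These rates rest on an equal-variance binormal model and on the day 4/day 21 planning case. They are not estimates for days 7 or 11, other endpoints or change scores; section 1.2.1 itself reports similar performance of the two tests on the later day in the earlier study. The overall ranking of the tests is almost never reversed, and the primary conclusion does not depend on any of this. It is a cheap improvement to the secondary analyses.

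**What to change.** In 7.6.2, for objectives 4 and 5:

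- Keep the Youden thresholds, labelled as descriptive cut-offs.
- Add the paired difference in sensitivity between hhCG and hCG+β at a common specificity fixed in advance (80% or 90%, for example), with a 95% patient-level bootstrap interval that re-derives both thresholds in each resample.
- Give the PPV and NPV differences at the same operating point, with intervals obtained the same way.

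State one cut-off rule in both 7.4 and 7.6.2. Extend the same method to the change scores of objectives 8 and 9. Do not rely on a paired test at the two separate Youden cut-offs.

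The cost is a few lines of text and some bootstrap code, with no new data. The specificity must be chosen before the data are seen. A very high value is less stable: at 95% the threshold rests on about 4 of the 75 negatives (75 × 0.05 = 3.75). The intervals will be wide: the simulated SD of the sensitivity difference at 80% specificity is 0.098, so the half-width at day 4 is about 1.96 × 0.098 = 0.19, or roughly ±20 points.
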